12.8 Sample size calculation

12.8.1 Primary endpoint(s)

The sample size of 20 participants per arm is selected based on budget and need for early availability of results for the current influenza season. This sample size of 20 subjects will provide estimates of proportion responded with margin of error (half-width of a 95% confidence interval) of 20.1%, 19%, and 17.5% corresponding to response rates of 70%, 75%, and 80%, respectively. Adjusting for 10% drop-out, 22 subjects will be enrolled in each arm.

13 Ethical considerations and administrative procedures

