Key safety assessments	Primary: Seroprotection as defined by a postvaccination antibody titer ≥ 40 (yes/no)	
	Secondary:	
	Seroconversion as defined by either:	
	 ≥ 4-fold increase in HI titers after vaccination (in participants with prevaccination HI titers ≥10) (yes/no) or 	
	 postvaccination HI titers ≥40 (in participants with prevaccination HI titers < 10) (yes/no) 	
	2. Change in HI titers	
	AEs, SAEs, events leading to discontinuation	
Data analysis	Sample size calculations were based on the proportion of subjects who responded to influenza vaccination.	
	The sample size of 20 participants per arm is selected based on budget and need for early availability of results. The sample size of 20 subjects will provide estimates with margin of error (half-width of a 95% confidence interval) of 20.1%, 19%, and 17.5% corresponding to response rates of 70%, 75%, and 80%, respectively. Adjusting for 10% drop-out, 22 subjects will be enrolled in each arm.	
Key words	Influenza, vaccine, ofatumumab, HI titer, open-label	

1 Introduction

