12.4.2 Statistical model, hypothesis, and method of analysis

The number and percentage of responders by year of enrolment in study and overall will be presented. The 95% confidence interval for the proportion of responders will be calculated by using exact method.

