12.5 Analysis of secondary endpoint(s)/estimand(s)

The secondary endpoint is achieving seroconversion defined as meeting one of the following two criteria:

- ≥ 4-fold increase in HI titers after vaccination (in participants with prevaccination HI titers ≥10) (yes/no) or
- postvaccination HI titers ≥40 (in participants with prevaccination HI titers < 10) (yes/no)

Proportion of participants achieved seroconversion at Week 4 will be estimated and the corresponding 95% confidence interval will be calculated using exact method.

Both non-responder imputation and observed case approaches will be applied in the analyses of seroconversion.

To assess the change in HI titers, geometric means will be calculated for pre- and post-vaccination HI titers.

To meet European Medicines Agency guidelines for protection for the Cohort, at least one of the following criteria has to be met:

- 1. Seroprotection rate is better than 70%;
- 2. Seroconversion rate is higher than 40%;
- 3. Ratio of geometric mean of post- to pre-vaccination HI titers ≥ 2.5 .

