2.5.2 Statistical hypothesis, model, and method of analysis

The number and percentage of responders will be presented. A 95% confidence interval for the proportion of responders will be calculated using an exact method.

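### The stated margins of error at n = 20 are normal-approximation half-widths, but both documents plan an exact interval and do not say which one.

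*Protocol*

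**What the plan says.** Protocol 12.8.1 explains the sample size in two steps. The number itself is pragmatic: "The sample size of 20 participants per arm is selected based on budget and need for early availability of results for the current influenza season". Its consequence is then given as a "margin of error (half-width of a 95% confidence interval) of 20.1%, 19%, and 17.5% corresponding to response rates of 70%, 75%, and 80" per cent. The Data analysis row of the protocol summary has the same figures ("The sample size of 20 subjects will provide estimates with margin of error (half-width of a 95% confidence interval) of 20.1%, 19%, and 17.5" per cent), and so does SAP 3. None of the three places says which interval formula lies behind the margins.

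The analysis sections specify a different kind of interval from the one these margins describe:

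- Protocol 12.4.2, seroprotection: "The 95% confidence interval for the proportion of responders will be calculated by using exact method".
- Protocol 12.5, seroconversion: "the corresponding 95% confidence interval will be calculated using exact method".
- SAP 2.5.2, seroprotection: "A 95% confidence interval for the proportion of responders will be calculated using an exact method". SAP 2.7.2 uses the same sentence for seroconversion.

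Neither document names the exact method.

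**The concern.** Symmetric margins of 20.1, 19 and 17.5 points at n = 20 look like the simple normal approximation. An exact binomial interval at 70 to 80% is not symmetric, because it reaches further down than up, so no single half-width describes it. If the margins come from one formula and the reported interval from another, the plan promises a precision that the analysis may not show.

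This is a pure estimation study. It tests no hypothesis, and the primary result is a proportion with its 95% interval. The margins are the only quantitative statement of what 20 participants per cohort will deliver. The lower limit is the informative side, because the question is whether treated participants mount an adequate response, and a symmetric margin makes that side look better than it will be.

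Not naming the method is a second gap. Several intervals can properly be called exact, and they differ by more than a point at this sample size. The study is open-label with planned interim readouts, so the choice should be fixed in writing before the final analysis.

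**Working it through.** **Inputs.** n = 20 per cohort, a 95% confidence level, and response rates of 70%, 75% and 80% (14, 15 and 16 of 20), all from Protocol 12.8.1. The reported interval is exact, method unnamed (Protocol 12.4.2 and 12.5, SAP 2.5.2 and 2.7.2).

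**Step 1: reproduce the stated margins.** Wald half-width = 1.96 × √(p(1−p)/n).

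- 70%: 1.96 × √(0.70 × 0.30/20) = 20.08 points (stated 20.1)
- 75%: 1.96 × √(0.75 × 0.25/20) = 18.98 points (stated 19)
- 80%: 1.96 × √(0.80 × 0.20/20) = 17.53 points (stated 17.5)

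All three agree after rounding. Wilson, Agresti-Coull, Jeffreys, mid-P, Clopper-Pearson (at the observed count and in expectation), inversion of the binomial test, continuity-corrected Wald and a t-based interval were also tried. None of them gives all three figures.

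**Step 2: Clopper-Pearson at the same n (assumed method).** For x responders out of n, the lower limit is the 2.5% quantile of Beta(x, n−x+1) and the upper limit is the 97.5% quantile of Beta(x+1, n−x).

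| Responders | 95% limits | Half-width | Below / above estimate | Stated margin | Excess |
|---|---|---|---|---|---|
| 14/20 (70%) | 45.7 to 88.1% | 21.2 | 24.3 / 18.1 | 20.1 | 1.1 |
| 15/20 (75%) | 50.9 to 91.3% | 20.2 | 24.1 / 16.3 | 19 | 1.2 |
| 16/20 (80%) | 56.3 to 94.3% | 19.0 | 23.7 / 14.3 | 17.5 | 1.5 |

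The excess is measured against the rounded margins in the plan. Against the unrounded Wald values it is 1.1, 1.2 and 1.4 points.

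**Step 3: the lower limit.** Read as symmetric margins, the plan's figures imply lower limits of 70 − 20.1 = 49.9%, 75 − 19 = 56.0% and 80 − 17.5 = 62.5%. The Clopper-Pearson limits are lower by 49.9 − 45.7 = 4.2, 56.0 − 50.9 = 5.1 and 62.5 − 56.3 = 6.2 points.

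**Step 4: range over the unnamed method.** Blaker's exact interval, by grid inversion, gives about 47.4 to 86.1%, 52.6 to 89.6% and 57.8 to 92.9%, with half-widths of about 19.3, 18.5 and 17.5 points. These are at or below the stated margins. Inverting the two-sided binomial test gives 19.3, 18.5 and 17.6 points. The sign of the half-width discrepancy therefore depends on the method. The asymmetry does not: Blaker's lower limits are still 49.9 − 47.4 = 2.5, 56.0 − 52.6 = 3.4 and 62.5 − 57.8 = 4.7 points below those that the symmetric margins imply.

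**The case against.** The strongest reply is that nothing has been miscalculated. The margins are correct for the formula that produced them, the plan speaks only of a 95% confidence interval at that point, and a normal approximation is common shorthand for planned precision. Nothing turns on it either. The sample size came from budget and timing, there is no hypothesis test, and the EMA criteria in Protocol 12.5 and SAP 2.7 are worded on rates and a geometric mean ratio, with no confidence limit. This stands, and it caps the importance of the point. It does not answer the mismatch, because the shorthand is not labelled as such and the reader is told about an interval that will not be reported.

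A second reply is that the stated margins are too narrow only under Clopper-Pearson. That is right, and it is the reason for asking that the method be named.

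A third is that the primary denominator may not be 20. Missing titers count as non-response (Protocol 12.4.4, SAP 2.5.3), the SAP's Safety Set takes in vaccinated participants, and 22 per cohort are to be enrolled. With 22 in the denominator and the same observed rates (treating n × p as continuous), Clopper-Pearson half-widths are 20.2, 19.3 and 18.1 points, only 0.1, 0.3 and 0.6 above the stated margins. The offset is partial, because imputed non-responders also lower the observed rate: 14 of 22 gives 21.1 points. The plan bases its own precision statement on 20, so 20 is the right basis for checking it. Any replacement text should state its denominator.

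**Conclusion.** The point holds. The margins in the protocol summary, Protocol 12.8.1 and SAP 3 are Wald half-widths, while every section that specifies the analysis plans an exact interval without naming it. If the method is Clopper-Pearson and the denominator is 20, the half-widths are 1.1 to 1.5 points wider than stated and the lower limits are 4.2 to 6.2 points below those implied by symmetric margins. With Blaker's interval the half-widths are at or slightly below the stated figures, but the interval is still asymmetric.

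This is a mismatch between the precision statement and the planned analysis. It is not an error in the sample size. The effect is modest and changes no decision in the plan. It should still be corrected, because in a study that only estimates, the planned precision should be that of the interval to be reported.

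**What to change.** In the protocol summary, Protocol 12.8.1 and SAP 3, replace the three margins with text such as:

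> With 20 participants in the denominator, the two-sided exact (Clopper-Pearson) 95% confidence interval is 45.7% to 88.1% for 14/20 (70%), 50.9% to 91.3% for 15/20 (75%) and 56.3% to 94.3% for 16/20 (80%).

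Name Clopper-Pearson also in Protocol 12.4.2 and 12.5 and in SAP 2.5.2 and 2.7.2. If the sponsor intends another exact method, name that one throughout and give its limits instead. The least that would do is to label the present margins as normal approximations and name the exact method in each document, but that leaves the asymmetry undescribed.

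The cost is wording in both documents. The sample size and the analysis stay as they are. The only downside, under Clopper-Pearson, is a slightly less favourable statement of precision.

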13.1 Regulatory and ethical compliance

This clinical study was designed and shall be implemented, executed and reported in accordance with the ICH Harmonized Tripartite Guidelines for Good Clinical Practice, with applicable local regulations (including European Directive 2001/20/EC, US CFR 21), and with the ethical principles laid down in the Declaration of Helsinki.

13.2 Responsibilities of the investigator and IRB

Before initiating a trial, the investigator/institution must obtain approval/favorable opinion from the IRB for the trial protocol, written informed consent form, consent form updates, participant recruitment procedures (e.g., advertisements) and any other written information to be provided to participants. Prior to study start, the investigator is required to sign a protocol signature page confirming his/her agreement to conduct the study in accordance with these documents and all of the instructions and procedures found in this protocol and to give access to all relevant data and records to Novartis monitors, auditors, Novartis Quality Assurance representatives, designated agents of Novartis, IRBs, and regulatory authorities as required. If an inspection of the clinical site is requested by a regulatory authority, the investigator must inform Novartis immediately that this request has been made.

13.3 Publication of study protocol and results

The protocol will be registered in a publicly accessible database such as clinicaltrials.gov and as required in EudraCT. In addition, after study completion (*defined as last patient last visit*) and finalization of the study report the results of this trial will be submitted for publication and posted in a publicly accessible database of clinical trial results, such as the Novartis clinical trial results website and all required Health Authority websites (e.g. Clinicaltrials.gov, EudraCT etc.).

For details on the Novartis publication policy including authorship criteria, please refer to the Novartis publication policy training materials that were provided to you at the trial investigator meetings.

13.4 Quality Control and Quality Assurance

Novartis maintains a robust Quality Management System (QMS) that includes all activities involved in quality assurance and quality control, to ensure compliance with written Standard Operating Procedures as well as applicable global/local GCP regulations and ICH Guidelines.

Audits of investigator sites, vendors, and Novartis systems are performed by auditors, independent from those involved in conducting, monitoring or performing quality control of the clinical trial. The clinical audit process uses a knowledge/risk based approach.

Audits are conducted to assess GCP compliance with global and local regulatory requirements, protocols and internal SOPs, and are performed according to written Novartis processes.

14 Protocol adherence

This protocol defines the study objectives, the study procedures and the data to be collected on study participants. Additional assessments required to ensure safety of participants should be administered as deemed necessary on a case by case basis. Under no circumstances including incidental collection is an investigator allowed to collect additional data or conduct any additional procedures for any purpose involving any investigational drugs under the protocol, other than the purpose of the study. If despite this interdiction prohibition, data, information, observation would be incidentally collected, the investigator shall immediately disclose it to Novartis and not use it for any purpose other than the study, except for the appropriate monitoring on study participants.

Investigators ascertain they will apply due diligence to avoid protocol deviations. If an investigator feels a protocol deviation would improve the conduct of the study this must be considered a protocol amendment, and unless such an amendment is agreed upon by Novartis and approved by the IRB and Health Authorities, where required, it cannot be implemented.

DMS Document Management System EMA European Medicines Agency

EOS End of Study
FAS Full Analysis Set

GPS Global Statistical and Programming Environment

HI Hemagluttination Inhibition

IA Interim Analyses
MS Multiple Sclerosis

MedDRA Medical Dictionary for Drug Regulatory Affairs

NRI Non-responder Imputation

PK Pharmacokinetics

PRO Patient-reported Outcomes

PT Preferred Term

QIV Quadrivalent inactivated influenza vaccine

RAP Reporting & Analysis Process
RMS Relapsing Multiple Sclerosis
SAE Serious Adverse Event
SAF Safety Analysis Set
SAP Statistical Analysis Plan
SAS Statistical Analysis System

sc Subcutaneous

SOC System Organ Class

TEAE Treatment Emergent Adverse Events

TFLs Tables, Figures, Listings

iDMT Injectable Disease Modifying Therapy

1 Introduction

The purpose of this Statistical Analysis Plan (SAP) is to describe the statistical methods planned in Section 12 of the Clinical Study Protocol (CSP) version 00 (release date 10 November 2020) for the clinical trial COMB157GUS12 and any additional analyses, specifications or deviations from this planned protocol before clinical database lock (CDBL).

This SAP will be used to draft the Clinical Study Report (CSR) Section 9.7: Statistical methods and IA plans.

1.1 Study design

This is a three-cohort, multicenter prospective study in up to 66 participants with relapsing multiple sclerosis (RMS).

Cohorts 1 and 2 will include up to 44 participants who will either begin treatment with ofatumumab (Cohort 1) or who are already treated with commercial ofatumumab (Cohort 2). Participants in **Cohort 1** will receive the inactivated influenza vaccine two weeks prior to starting treatment with ofatumumab, while participants in **Cohort 2** will receive the inactivated influenza vaccine after at least 4 weeks of commercial ofatumumab treatment.

Cohort 3 will include the remaining 22 participants who are already treated with commercial injectable disease modifying therapy (iDMT) and who will receive the inactivated influenza vaccine after at least 4 weeks of commercial iDMT treatment.

The study consists of three periods:

- Screening Period (1 week);
- Investigational Period (4 weeks);
- Optional, 6-month open-label Extension Period

Screening Period

Participants will enter a Screening Period of up to 1 week to assess eligibility requirements. Participants in Cohort 1 without Hepatitis B virus (HBV) and serum immunoglobulin results within the past 6 months prior to screening will require central labs drawn. Participants with Hepatitis B virus (HBV) and serum immunoglobulin results within the past 6 months prior to screening will not require the labs to be drawn.

Investigational Period

All participants will receive the inactivated influenza vaccine before or during the Week 0 visit, but within 9 calendar days after their screening visit.

- Participants in **Cohort 1**: Loading doses of ofatumumab will be administered at Week 2, 3 and 4.
- Participants in Cohort 2 will continue taking their prescribed of atumumab as per their dosing schedule throughout the investigational period.
- Participants in **Cohort 3** will continue administration of their prescribed iDMT as per their dosing schedule throughout the investigational period.

Optional, 6-month open-label Extension Period

- Participants in **Cohort 1** will administer their first dose of ofatumumab in the open-label Extension Period at Week 6. Thereinafter, they will continue monthly dosing until the final dose at Week 26. Novartis will supply ofatumumab to participants in Cohort 1 for the Extension Period.
- Participants in Cohort 2 will continue to administer of atumumab monthly until the final dose at Week 28. Novartis will supply of atumumab to participants in Cohort 2 for the open-label Extension Period.
- Participants in **Cohort 3** will not have the option to enter this Extension Period.

Study completion

For participants completing the trial, the total duration of the trial will be a minimum of 5 weeks. This accounts for the mandatory 1 week Screening Period and 4 week Investigational Period starting at Week 0. Upon completing the Investigational Period, participants in Cohorts 1 and 2 will have the option to enter a 6 month open-label Extension Period, where they will continue monthly dosing of ofatumumab. Participants in cohort 3 will not enter the Extension Period.

Cohort 1 and 2 participants who prematurely discontinue the study while in the Investigational Period should be scheduled for the End of Study (EOS1) visit within 7 days. Cohort 3 participants who prematurely discontinue the study while in the Investigational Period should be scheduled for the End of Study (EOS) visit within 7 days. Cohort 1 and 2 participants who prematurely discontinue the study while in the Extension Period should be scheduled for the final visit of the extension period (EOS2) within 7 days. All EOS assessments should be performed except study drug administration.

Study design schematics for Cohorts 1, 2 and 3 are shown in Figure 1-1, Figure 1-2 and Figure 1-3 and respectively.

Primary analysis time point

The primary analysis time point will be Week 4.

Interim analysis

An interim analysis (IA) will be performed after all participants complete the Investigational Period or discontinue the Investigational Period prematurely, or on/around March 29, 2021, whichever comes first.

Figure 1-1 Study Design (Cohort 1)

[figure not shown]

Figure 1-2 Study Design (Cohort 2)

[figure not shown]
[figure not shown]

Figure 1-3 Study Design (Cohort 3)

1.2 Study objectives and endpoints

Study objectives and associated endpoints are shown in Table 1-1.

Table 1-1 Study objectives and endpoints

Objective(s) Endpoint(s) Primary objectives(s) Endpoint(s) for primary objective(s) To characterize those achieving Achieving seroprotection as defined by a seroprotection after receiving the 2020post-vaccination antibody titer ≥40 at 2021 seasonal quadrivalent influenza Week 4 (yes/no) vaccine in participants treated with ofatumumab 20 mg sc once every 4 weeks Secondary objective(s) Endpoint(s) for secondary objective(s) To characterize those achieving Achieving seroconversion at Week 4 as seroconversion after receiving the 2020defined by either: 2021 seasonal quadrivalent influenza a. a ≥4-fold increase in HI titers vaccine in participants treated with after vaccination (in participants ofatumumab 20 mg sc once every 4 with pre-vaccination HI titers weeks ≥10) or Safety

Objective(s)	Endpoint(s)
	b. post-vaccination HI titers ≥40 (in participants with pre-vaccination HI titers <10) (yes/no)
	 Change in HI titers
	 AEs, SAEs, AEs leading to discontinuation

2 Statistical methods

2.1 Data analysis general information

The statistical analysis outlined in this SAP will be performed by Novartis or a designated Contract Research Organization (CRO), using SAS® version 9.4 or higher and stored in the Novartis Global Programming and Statistical Environment (GPS).

For continuous variables, summary statistics will include number of participants (n), mean, standard deviation, minimum, maximum, median and 25th and 75th percentiles (optional). For categorical variables, frequency counts and percentages will be reported.

Unless otherwise stated, all data summaries will be presented by cohort and on all participants in the respective analysis set.

The CSR analysis cut-off date will be the EOS1/EOS visit for participants who do not continue to the Extension Period, or the EOS2 visit for participants who continue into the Extension Period. All data collected prior to this date will be used for analysis.

All data (collected or derived) will be listed appropriately.

2.1.1 General definitions

Treatment of interest

The investigational treatment or treatment of interest will refer to a once-off administration of the 2020-2021 quadrivalent inactivated influenza vaccine (QIV) via 0.5-mL single-dose prefilled syringe to participants in all three cohorts.

Additional treatment

- Ofatumumab provided by Novartis in an auto-injector containing 20 mg sc ofatumumab (20 mg/0.4ml) for subcutaneous administration to participants in Cohort 1 in the Investigational and optional Extension Periods and to participants in Cohort 2 entering the optional open-label extension period as per the assessment schedule.
- Ofatumumab as commercially prescribed in the course of medical practice for participants in **Cohort 2** for the Investigational Period.
- Any MS iDMT as commercially prescribed in the course of medical practice for participants in **Cohort 3**.

Study day

The day of Week 0 visit is defined as Study Day 1 or Day 1. All other study days will be labeled relative to Day 1.

For event dates **on or after Day 1**, study day for a particular event date is calculated as:

(Date of event - date Week 0 visit) + 1

I.e. Day 2, Day 3, etc., will be one day, two days, etc., after Day 1, respectively.

For dates **before Day 1**, study day for an event date is calculated as:

(Date of event – date Week 0 visit)

Duration of an event will be calculated as (event end date – event start date + 1).

The descriptor "Day 0" will not be used.

Screening, baseline and post-baseline definitions

Screening refers to any procedures (e.g., checking inclusion and exclusion criteria) performed prior to vaccination. Per protocol, participant informed consent must be obtained prior to performing any study related activity. The date of signing of informed consent is the start date of the screening period. Any assessment obtained during the screening period will be labelled screening assessment.

Baseline is the last assessment (including unscheduled visits) obtained before the date of vaccination. No visit windows will be needed for the identification of baseline assessment. All assessments obtained after the date of vaccination are considered as **post-baseline** unless otherwise specified.

Nominal visits

Nominal visits are defined as all scheduled visits as per the clinical study protocol including the EOS visits. The definition of nominal visit excludes unscheduled visits.

Change from baseline

Change from baseline will be calculated as:

(Post-baseline value – baseline value)

Change from baseline will only be calculated and summarized for participants with both baseline and post-baseline values.

